Inclusion Criteria 
1. Evidence of a personally signed and dated informed consent document indicating that the subject (or a legally authorized representative) and caregiver/informant has been informed of all pertinent aspects of the study. Participants must be able to provide consent or assent (where this is in accordance with local laws, regulations and ethics committee policy) and consent/assent must be re-evaluated during the study at regular intervals.2. Male or female subjects aged 50-85 years (inclusive) at Screening Visit.3. Female subjects must be of non-child-bearing potential. Male subjects with female partners of childbearing potential must agree to acceptable birth control for the duration of the study and for 90 days thereafter.4. If on pharmacological treatment for diabetes, must be on stable dose for at least 60 days prior to screening and remain stable through Baseline. There should be expectation that treatment and dose will remain stable during the study period.5. Clinical diagnosis of probable Alzheimer's disease, consistent with the criteria from the 2011 National Institute on Aging and Alzheimer's Association workgroup [McKhann 2011], for at least 2 months prior to Screening. Evidence of progression must be documented in source documentation at the time of screening based on review of prior medical records and/or information gathered from the subject or caregiver/informant(s).6. Mini-Mental State Exam (MMSE) score of 21-26 inclusive at Screening and 19-27 at Baseline.7. CDR global score of 0.5 or 1 at Screening and Baseline.8. ADAS-cog14 score of ≥ 10 at Screening and Baseline.		

Study Number: TPP488-305	Phase: 2/3	

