Assuming a standard deviation of the change from Baseline to Month 18 in ADAS-cog14 of 7.5, using alpha = 0.049, a total sample size of 120 subjects in balanced allocation (60 subjects per group) provides at least 90% power to detect a difference between treatment groups of 4.5 using a 2-sided, 2-sample t-test. Assuming a dropout rate of 25% or less, randomization of 160 subjects provides adequate statistical power for Part 2 to demonstrate superiority of azeliragon over placebo based on the ADAS-cog14.		
Statistical methods:		
The primary analysis will use the intent-to-treat (ITT) methodology and a main-effects model for analysis of covariance with baseline ADAS-cog14 as a covariate on change from baseline to endpoint in ADAS-cog14 using multiple-imputation methods for coping with missing data. The primary analysis will be supported by a mixed-models repeated measures (MMRM) analysis with adjustment for baseline ADAS-cog14 measures. Similar methodology will be used for the functional endpoints (CDR-sb, FAQ, Amsterdam IADL). The primary analysis will also be supported by ANCOVA using last-observation-carried-forward (LOCF) methods, and also an observed cases analysis (no imputation, no deletion) will be done. The supportive MMRM analysis will include treatment, time and treatment-by-time interaction as fixed effects, baseline as covariate and subject as a random effect. Supportive modeling will also include MMRM main-effects model with treatment, time, and subject. The same statistical methodology will be applied to the functional endpoints. A conditional sequence of statistical hypotheses will be used to control alpha with the ADAS-cog14 being tested first, and conditional on statistical significance, testing will proceed to CDR.		

Study Number: TTP488-305	Phase: 2/3	
Descriptive summaries will be produced of the observed values and change from baseline in co-primary variables by treatment group at each individual time point and at endpoint (final on-treatment assessment for each subject).		
In accordance with FDA guidance on adaptive studies, the planned features of the confirmatory phase (Part 2) are pre-specified. The features subject to modification informed by the learning phase of the study (Part 1) are:		

• Primary endpoint for Part 2• Sample size for Part 2• Study duration for Part 2• Eligibility for Part 2• Dose of study drug for Part 2		

Table 1. Part 1 Schedule of Activities

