4.0 SUBJECT SELECTION**4.1 INCLUSION CRITERIA**

Subject eligibility must be reviewed and documented by an appropriately qualified member of the Principal Investigator's (PI's) study team before participants are included in the study.

1. Evidence of a personally signed and dated informed consent document indicating that the subject (or a legally authorized representative) and caregiver/informant has been informed of all pertinent aspects of the study. Participants must be able to provide consent or assent (where this is in accordance with local laws, regulations and ethics committee policy) and consent/assent must be re-evaluated during the study at regular intervals.
2. Male or female subjects aged 50-85 years (inclusive) at Screening Visit.
3. Female subjects must be of non-childbearing potential. Male subjects with female partners of child bearing potential must agree to acceptable birth control for the duration of the study and for 90 days thereafter.
4. If on pharmacological treatment for diabetes, must be on stable dose for at least 60 days prior to screening and remain stable through Baseline. There should be expectation that treatment and dose will remain stable during the study period.
5. Clinical diagnosis of probable Alzheimer's disease, consistent with the criteria from the 2011 National Institute on Aging and Alzheimer's Association workgroup [McKhann 2011], for at least 2 months prior to Screening. Evidence of progression must be documented in source documentation at the time of screening based on review of prior medical records and/or information gathered from the subject or caregiver/informant(s).
6. Mini-Mental State Exam (MMSE) score of 21-26 inclusive at Screening and 19-27 at Baseline.
7. CDR global score of 0.5 or 1 at Screening and Baseline.
8. ADAS-cog14 score of ≥ 10 at Screening and Baseline.

9. Participant must be on a stable dose of a background cholinesterase inhibitor and/or memantine (approved by relevant health authority where trial is being conducted) at least 60 days prior to Screening and remain stable through Baseline. There must be agreement not to change the treatment or dose during the study period unless the investigator judges that the dose needs to be reduced or stopped due to a safety and/or tolerability reason.
10. Hemoglobin A1c (HbA1c) 6.5% - 9.5%, inclusive, at Screening.
11. Body mass index (BMI) 19.0 – 37.0 kg/m², inclusive, at Screening Visit and Baseline Visit.

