For logistical purposes, up to 60 days will be allowed for screening to confirm that participants meet all selection criteria for the study. It is strongly encouraged that the screening period is minimized to the shortest possible duration whenever possible. The investigator (or an appropriate delegate at the investigator site) will obtain informed consent from each subject, caregiver/informant, and when appropriate, legally authorized representative in accordance with Subject Information and Informed Consent/Accent (where this is in accordance with local laws, regulations and ethics committee policy). The screening assessments may be separated out into more than one visit if required. Refer to the Schedule of Events for a tabular presentation for screening activities ([Table 1](#), [Table 2](#)).

The following activities will be completed:

- Complete informed consent/assent process (where this is in accordance with local laws, regulations and ethics committee policy) resulting in a signed ICF(s) by the appropriate parties.
- Assign screening identification number.
- Fasting blood and urine specimens for safety laboratory tests (serum chemistry, hematology, UA) will be collected, in addition to the following:
 - Plasma glucose and HbA1c
 - Hepatitis screens (including hepatitis B surface antigen, hepatitis B core antibody, hepatitis B surface antibody, and hepatitis C antibody)
 - Thyroid function (T3, T4, and TSH)
 - Vitamin B12
 - Serum FSH concentrations in all female participants to confirm post-menopausal status and eligibility regarding non-child bearing potential
 - Urine drug screen

- Provide subject with a meal/snack.
- Check blood sugar, using point of care device, after an appropriate time.
 - If subject is hypoglycemic (<90mg/dL), feed the subject again and re-check blood sugar prior to neuropsychological assessments.
 - If subject is hyperglycemic (>300mg/dL), reschedule the neuropsychological assessments for a proximal day within the visit window.
- MMSE.
- ADAS-cog14.
- CDR (calculation of both global score and sum of boxes score).
- Columbia Suicide Severity Scale (C-SSRS).
- Demographic information (i.e., sex, date of birth, race/ethnicity).
- Complete medical and surgical history, including family medical history of dementia.
- History of prior participation and dosing in a clinical trial.
- Record and review all prior medications for Alzheimer's disease.

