9.7.2 Statistical Methodology for Primary Analysis

The primary analysis will use the ITT methodology and a main-effects mixed-models for repeated measures (MMRM) methodology. The MMRM will utilize an unstructured covariance where the number of parameters is “ $t(t+1)/2$ ” where “ t ” is the dimension of the covariance matrix, using PROC MIXED in SAS. In the unlikely event of lack of convergence, Toeplitz structure will be employed where the number of parameters is “ t ” where “ t ” is the dimension of the covariance matrix. Time is considered as a class variable. Analysis will include treatment, time and treatment-by-time interaction as fixed effects, Baseline as covariate, and subject as a random effect. Supportive modeling will also include MMRM main-effects model with treatment, time, and subject.

Model assumptions will be evaluated. If the parametric assumptions are evaluated as inappropriate or violated, rank analogues will be advanced.

The primary analysis will be done for each stage separately. Part 1 will use alpha = 0.0499, which includes an adjustment of 0.0001 for interim analyses performed by the Independent Data Monitoring Committee (IDMC). The alpha adjustment for the IDMC for Part 1 is considered to be negligible, hence, the stated alpha for Part 1 is 0.05 for the 100-patient, 6-month trial. Part 2 will use alpha = 0.049, which includes an adjustment of 0.001 for interim analyses performed by the Independent Data Monitoring Committee (IDMC), thereby preserving the overall study-wise alpha = 0.05. The alpha adjustment of 0.001 is considered to be appropriate for the 200-patient, 18-month study.

Multiple imputations (MI) will be used as a supportive analysis with 100 invocations (acknowledging that more invocations are needed with more missing data). Monte Carlo methods are planned.

An essential component of the thorough analysis includes an assessment of the impact of missing data on study conclusions. As a part of assessing this impact, supportive analysis will include:

- an endpoint analysis (reduction to last-observation-carried-forward, justified in this study based on the monotonic progression of the natural course of AD and assuming no more dropouts in the group treated with azeliragon than in the group treated with placebo)
- a completers analysis (observed cases at endpoint)
- observed cases by assessment time.

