1.10 Adaptive Study

This study is an adaptive trial, which includes 2 studies under the same protocol. This SAP is focused on Part 1 of this adaptive study.

This SAP conforms to standards set forth in *Adaptive Designs for Clinical Trials of Drugs and Biologics Guidance for Industry* (CDER, CBER, November 2019). The intention of the adaptive nature of this protocol is to leverage potential advantages related to statistical analysis as depicted in the FDA final guidance.

2 Statistical Hypotheses

Part 1 has a single primary endpoint (ADAS-Cog14).

The testing sequence will be as follows for strict significance, however proof of concept will be attained by significance in any of the outcomes below (Figure 1):

The first set of hypotheses to be tested is as follows:

H₀₁: The mean change in ADAS-cog14 in the active group is equal to that of the placebo group*.

H₁₁: The mean change in ADAS-cog14 in the active group is not equal (is superior) to that of the placebo group*.

Conditional on statistical significance, testing will proceed hierarchically:

H₀₂: The mean change in A-IADL in the active group is equal to that of the placebo group.

H₁₂: The mean change in A-IADL in the active group is not equal (is superior) to that of the placebo group[§].

Conditional on statistical significance, testing will proceed:

H₀₃: The mean change in CDR-sb in the active group is equal to that of the placebo group.

H₁₃: The mean change in CDR-sb in the active group is not equal (is superior) to that of the placebo group[§].

Conditional on statistical significance, testing will proceed:

H₀₄: The mean change in FAQ in the active group is equal to that of the placebo group.

H₁₄: The mean change in FAQ in the active group is not equal (is superior) to that of the placebo group[§].

H₀₅: The mean change in the cognitive composites or GST in the active group is equal to that of the placebo group.

H₁₅: The mean change in the cognitive composites or GST in the active group is not equal (is superior) to that of the placebo group.

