6.2 Statistical Methodology for Efficacy Analysis

The primary analysis will use the ITT methodology and a mixed-model measures (MMRM) methodology with a random slope and intercept for each individual. The MMRM will utilize an

unstructured covariance with only one parameter for the correlation between the slope and intercept. Time (ADY) is considered as a continuous variable. Analysis will include baseline risk score, treatment, time, as well as HbA1C by treatment, treatment-by-time, baseline by treatment, and baseline by time interactions as fixed effects. Subject will be included as a random effect. Baseline visit will be included in the model. Baseline risk score is derived from the historic STEADFAST data and calculated as a linear calculation of:

$$age*-0.03582 + hba1c*-0.2335 + mmsebl*-0.2683 + base*-0.09342$$

First the baseline risk score will be subtracted from the change score for each individual. Then the mean baseline value of the risk adjusted change score will be calculated separately for each treatment group. Finally, the risk adjusted change scores for each individual will have their group mean added back in to ensure an average score of 0 at baseline for each group. This adjusted change score will be used in the model in place of change from baseline. Model assumptions will be evaluated. If the parametric assumptions are evaluated as inappropriate or violated, rank analogues will be advanced.

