8.1 Definition of Baseline

For safety evaluations, the Baseline assessment for all measurements will be the latest available, valid measurement taken prior to the initiation study medication, except for electrocardiography (ECG) values: The Baseline assessment for ECG include a triplicate assessment with the baseline value intended to be the arithmetic mean of the values taken at the Baseline assessment that are taken in triplicate. Baseline values for efficacy outcomes will be the average of screening and baseline visits where available. For the GST, the z-scores at each visit will be calculated using the mean over all patients of the average of screening and baseline, and using the standard deviation pooled across screening and baseline.

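### Part 2's primary models adjust for one baseline score per outcome although both co-primaries are scored twice before dosing; using both scores is a nearly free, modest gain in precision

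*Protocol*

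**What the plan says.** Two places in the protocol describe the primary model for Part 2.

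- Synopsis, Statistical methods: a "main-effects model for analysis of covariance with baseline ADAS-cog14 as a covariate on change from baseline to endpoint in ADAS-cog14", with multiple imputation.
- Section 9.7.2: an MMRM. "Analysis will include treatment, time and treatment-by-time interaction as fixed effects, Baseline as covariate, and subject as a random effect".

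They disagree on which method is primary, but both use the outcome's baseline as the only baseline covariate.

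A second pre-dose score exists for both co-primaries. Table 2 schedules ADAS-cog14 and CDR at Screening and at Baseline. Eligibility requires an "ADAS-cog14 score of ≥ 10 at Screening and Baseline" and a "CDR global score of 0.5 or 1 at Screening and Baseline". Section 6.1 asks for the CDR sum of boxes, as well as the global score, at Screening.

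SAP Section 8.1 uses both: "Baseline values for efficacy outcomes will be the average of screening and baseline visits where available". SAP Section 6.2 also includes a baseline-by-time term. But SAP Section 1.10 limits the scope: "This SAP is focused on Part 1 of this adaptive study". No Part 2 SAP is among the documents.

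**The concern.** A single pre-dose score contains visit-to-visit noise. The noisier the baseline covariate, the less of the Month 18 variance it explains, and the more is left in the standard error of the treatment difference. A second measurement before randomization reduces that noise, costs no extra visit, and cannot bias a randomized comparison.

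What is at stake is precision in the Part 2 co-primary analyses. It matters somewhat more than usual for two reasons. CDR-sb is a co-primary with no power calculation of its own, because Section 9.2 powers ADAS-cog14 only. Patients have also been hard to recruit: Part 1 enrolled 43 of a planned 100 (SAP Section 1.4).

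A smaller point concerns the MMRM only. As written, it fits one baseline slope common to all post-dose visits: six for ADAS-cog14 and four for CDR.

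**Working it through.** **The plan's own figure.** Section 9.2 gives a difference of 4.5, SD 7.5, two-sided alpha 0.049 and 60 per group. A two-sample t-test with the noncentral t distribution gives 90.2% power at 60 per group, and 120/(1 − 0.25) = 160 randomized. The stated size reproduces, and it credits no covariate. Section 3.0 plans 200 randomized instead; at 25% dropout that is 75 per group, with 95.4% power.

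**Inputs for the gain.** Only the change SD of 7.5 is in the protocol. Assumed: baseline SD sB = 7–8, Month 18 SD sY = 9.5–10.5, Screening–Baseline correlation r = 0.80–0.90.

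**Formulas.**
- Covariance of Baseline with Month 18: c = (sY² + sB² − 7.5²)/2, and ρ = c/(sY·sB).
- Residual variance with one baseline: sY²(1 − ρ²).
- With the mean of two equally predictive scores: sY²(1 − ρ²·2/(1 + r)).

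**Smallest gain** (sB 7, sY 9.5, r 0.90): c = (90.25 + 49 − 56.25)/2 = 41.5; ρ = 41.5/66.5 = 0.624. The residual variance goes from 55.10 to 53.25, so the SE ratio is √(53.25/55.10) = 0.983.

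**Largest gain** (sB 8, sY 10.5, r 0.80): c = (110.25 + 64 − 56.25)/2 = 59.0; ρ = 59/84 = 0.702. The residual variance goes from 55.86 to 49.82, so the SE ratio is 0.944.

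The standard error thus falls by 1.7–5.6%. In patients, 200 × (1 − 0.983²) ≈ 7 and 200 × (1 − 0.944²) ≈ 22.

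**If Screening predicts less well.** Screening can be up to 60 days before dosing. Let its correlation with Month 18 be ρs = ρ − d. Then:
- equal-weight mean: R² = (ρ + ρs)²/(2(1 + r));
- two separate covariates: R² = (ρ² + ρs² − 2ρρs·r)/(1 − r²).

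Reduction in SE against the single baseline, over the same SD ranges:

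| d | r | Mean of two | Both entered |
|---|---|---|---|
| 0 | 0.80 | 3.6–5.6% | 3.6–5.6% |
| 0 | 0.90 | 1.7–2.6% | 1.7–2.6% |
| 0.03 | 0.80 | 1.9–3.2% | 2.1–3.4% |
| 0.03 | 0.90 | 0.1–0.4% | 0.5–0.8% |
| 0.05 | 0.80 | 0.8–1.6% | 1.3–2.3% |
| 0.05 | 0.90 | about 1% loss | 0.1–0.2% |

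Entering both costs one degree of freedom. With about 150 evaluable patients and about 145 residual degrees of freedom, that is 1/(2 × 145) ≈ 0.3% of the SE, not deducted in the table.

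**Effect on power.** Multiplying SD 7.5 by 0.983 and by 0.944 gives 7.37 and 7.08. At 75 per group, power moves from 95.4% to 96.0–97.1%.

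**The case against.** The strongest reply is that nothing has been decided for Part 2. The protocol never defines Baseline for efficacy, and the synopsis refers to baseline measures in the plural when it describes the supportive MMRM. Section 9.0 says that the SAP supersedes the protocol and may be updated before Part 2 is unblinded. The definition of baseline belongs in a SAP, and the only SAP available already averages. This stands in part: the single score is inferred from the separate Baseline visit and the singular covariate, and a Part 2 SAP could adopt the average. But no such SAP is provided, and the analysis model is not among the Part 2 features listed as open to modification (synopsis and Section 9.1). If the text is read as silent, a definition is still needed.

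The second reply is that the gain is small and not assured. This stands too. At 200 randomized, power moves by about 1 to 2 points, and an equal-weight mean can lose about 1% if Screening is clearly the weaker predictor. Entering both scores avoids that loss, apart from one degree of freedom.

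A reader might also infer from the SAP Section 6.2 risk score ("age*-0.03582 + hba1c*-0.2335 + mmsebl*-0.2683 + base*-0.09342") that age, MMSE and HbA1c should be added in Part 2. The documents do not support a quantified gain. The coefficients have no stated time point. Assume SDs of 7–8 years, 1.7–2.2 MMSE points and 0.7–0.9% HbA1c, and independence. The summed squared coefficient × SD terms, divided by 7.5², then give R² of only 0.5–0.8%. After the cost of three covariates (3/(2 × 143) ≈ 1%), the SE would rise by 0.6–0.8%. A net gain of 1.4–2.8% appears only if the coefficients are tripled for Month 18, which nothing in the documents supports. It also treats MMSE as independent of baseline ADAS-cog14, another cognition score.

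**Conclusion.** The point holds as an efficiency improvement and no more. The Part 2 models, as written, leave unused a second pre-dose score that is already collected for both co-primaries and that the Part 1 SAP already uses.

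For ADAS-cog14 the Month 18 standard error would fall by 1.7–5.6% if Screening is as predictive as Baseline. If its correlation with Month 18 is 0.03–0.05 lower, the fall is about 0.1–3.4% with both scores entered separately, before the 0.3% for a degree of freedom. At the least favorable corner the net effect is therefore about zero or very slightly negative. All of this depends on assumed SDs and correlations that the documents do not give. For CDR-sb the same reasoning applies, but the documents give no SD from which to compute a figure.

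A reader might infer that the planned Part 2 analysis is flawed or undersized. It is neither on this account: baseline-adjusted ANCOVA or MMRM is valid, and 60 per group gives the stated power without any covariate.

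**What to change.** In the Part 2 SAP, or in a protocol amendment before Part 2 starts:

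- Define baseline for ADAS-cog14 and CDR-sb, and pre-specify that both the Screening and the Baseline scores are used. Either enter them as two covariates, which is safer if Screening is less predictive and costs one degree of freedom, or use their mean as in SAP Section 8.1, which costs none. If the mean is the covariate, compute the change score from that same mean; otherwise the calculation above does not apply.
- In the MMRM, let the baseline effect vary by visit, with one set of terms for each baseline score used. Section 9.7.2 says both that treatment-by-time is in the model and that the primary model has no interaction terms; reconcile these when adding the baseline-by-visit terms.
- Settle which model is primary (synopsis ANCOVA with multiple imputation, or Section 9.7.2 MMRM) and whether Part 2 randomizes 160 or 200.

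The cost is wording. Screening ADAS-cog14 is needed for eligibility and CDR-sb is already scored there, so no new data are required. FAQ and Amsterdam-IADL have no Screening score in Table 2 and would keep a single baseline.
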